4.5.1.3 Exposure during the Initial and Maintenance Treatment Period (combined)

Definitions for study medication duration (days) and time at risk (days) during the Initial and Maintenance Treatment Period (combined) are provided as follows:

Study medication duration (days)

Study medication duration will be summarized for BKZ 320mg Q4W, BKZ 320mg Q8W, and BKZ 320mg Total respectively:

- For BKZ 320mg Q4W:

Include study medication duration in ITP for study participants who are randomized to BKZ 320mg Q4W in ITP (refer to section 4.5.1.1 – study medication duration) and study medication duration in MTP for study participants who are randomized to placebo in ITP and switch to BKZ 320mg Q4W in MTP (refer to section 4.5.1.2 – study medication duration)

- For BKZ 320mg Q8W:

Include study medication duration in MTP for study participants who switch to BKZ 320mg Q8W in MTP (refer to section 4.5.1.2 – study medication duration)

- For BKZ 320mg Total:

For study participants randomized to BKZ 320mg Q4W in the ITP:

$\text{Date of last active dose} - \text{date of first dose in the ITP} + 28$ (if last active dose was in the ITP) or 56 (if last active dose was in the MTP)

- If the date of last active dose + 28 days (if last active dose was in the ITP) or 56 days (if last active dose was in the MTP) extends to a date beyond the date of last visit (including PEOT, not including SFU), then this calculation reverts to:

$\text{Date of last visit} - \text{date of first dose in the ITP} + 1$

- For study participants who died, if date of last active dose + 28 days (if last active dose was in the ITP) or 56 days (if last active dose was in the MTP) extends beyond the date of death, then this calculation reverts to:

$\text{Date of death} - \text{date of first dose in the ITP} + 1$

For study participants randomized to Placebo in ITP and switch to BKZ 320mg Q4W in MTP:

Include study medication duration in MTP defined in section 4.5.1.2 – study medication duration.

Time at risk (days)

Time at risk will be summarized for BKZ 320mg Q4W, BKZ 320mg Q8W, and BKZ 320mg Total respectively:

- For BKZ 320mg Q4W:

For study participants who are randomized to BKZ 320mg Q4W in ITP:

- For study participants who complete the final visit of the ITP (Week 16 visit) and continue to the MTP

Date of first dose in the MTP – date of first dose in the ITP + 1

- For study participants who died during the ITP

Date of death – date of first dose in the ITP + 1

- For study participants who discontinue the ITP early or who complete the ITP but do not continue to the MTP, use the minimum of the following:

Date of last dose in the ITP – Date of first dose in the ITP + 119

Date of last clinical contact – date of first dose in the ITP + 1

For study participants who are randomized to placebo in ITP and switch to BKZ 320mg Q4W in MTP:

Include time at risk in MTP defined in section 4.5.1.2 – time at risk.

- For BKZ 320mg Q8W:

Include time at risk in MTP for study participants who switch to BKZ 320mg Q8W in MTP (refer to section 4.5.1.2 – time at risk).

- For BKZ 320mg Total:

For study participants randomized to BKZ 320mg Q4W in ITP:

- For study participants who died before the final visit (not including SFU):

Date of death – date of first dose in the ITP + 1

- For all the other study participants including who discontinue early or who complete the MTP as scheduled, use the minimum of the following:

Date of last dose – Date of first dose in the ITP + 119

Date of last clinical contact – date of first dose in the ITP + 1

For study participants who are randomized to Placebo in ITP and switch to BKZ 320mg Q4W in MTP:

Include time at risk in MTP defined in section 4.5.1.2 – time at risk

A by-study participant listing of exposure to study medications will be provided on the SS by treatment group.

4.5.2 Adverse events

An AE is any untoward medical occurrence in a study participant or clinical investigation study participant administered a pharmaceutical product that does not necessarily have a causal

relationship with this treatment. An AE can therefore be any unfavorable and unintended sign (including an abnormal laboratory finding), symptom, or disease temporally associated with the use of a medicinal (investigational) product, whether or not related to the medicinal (investigational) product.

AEs will be coded according to the Medical Dictionary for Regulatory Activities (MedDRA version 19.0). All summaries will be provided by treatment group. The treatment group for each study participant will be defined as the treatment received at the onset of the AE. For study participants who switch treatment (ie, from placebo to bimekizumab or from bimekizumab Q4W to Q8W) at Week 16, any AEs that occur after initiation of the new treatment are attributable to the new treatment.

If an AE occurs on the date of a treatment switch, the event is attributed to the original treatment. The only exceptions are for the following types of events, which will be attributed to the new study treatment:

- Events that fulfill the anaphylaxis criteria for acute events (refer to Section 6.12)
- Events that fulfill the hypersensitivity reaction criteria (Hypersensitivity events will be identified using the “Hypersensitivity (Standardized MedDRA Query ([SMQ])”. All TEAEs which code to a Preferred Term (PT) included in the Scope=Narrow search will be included.)
- Events with a High Level Term (HLT) of “Administration site reactions NEC”
- Events with an HLT of “Injection site reactions”

4.5.2.1 Data considerations

TEAEs are defined as those AEs that have a start date on or following the first dose of IMP through the final dose of IMP + 119 days (covering the 17-week SFU period). If it is not possible (due to partial dates) to determine whether or not an AE is treatment-emergent then it will be assumed to be a TEAE.

The rules for imputing partial AE start or stop dates are described in Section 6.8.1.2.

If the intensity of an AE is unknown, it is considered as severe. If the relationship to study drug is missing, it is considered as related.

AEs will be presented as “number of study participants (percentage of study participants) [number of events]”. In this style of output, “[number of events]” will include all cases of an AE including repeat occurrences in individual study participants, while “number of study participants” will count each study participant only once.

AE summaries by System Organ Class (SOC), High Level Term (HLT) and Preferred Term (PT) will be ordered alphabetically for SOC and HLT within SOC and in terms of decreasing frequency for PT within HLT in the bimekizumab treatment group, and in the event of ties, PT will be sorted alphabetically.

AE summaries by PT will be ordered in terms of decreasing frequency for PT within the bimekizumab treatment group, and in the event of ties, PT will be sorted alphabetically.

Study participant time at risk represents the time a study participant is at risk for having an AE. The definitions for study participant time at risk (in days) are outlined in Section 4.5.1. These definitions will be used for exposure-adjusted AE summaries.

Selected AE summaries will include the exposure-adjusted incidence rate (EAIR) with associated 95% CI and the exposure-adjusted event rate (EAER).

The EAIR is defined as the number of study participants (n) with a specific AE adjusted for the exposure and will be scaled to 100 patient-years:

$$EAIR = 100 \times n / \sum_{i=1}^N (T_{Exp(i)})$$

where N is the total number of study participants in the respective treatment group, and $T_{Exp(i)}$ is the time of exposure for each study participant. If a study participant has the specific AE being summarized, the time of exposure is censored at the date of the event (calculated as AE start date – date of first IMP administration + 1). If a study participant has multiple events, the time of exposure is calculated to the first occurrence of the AE being considered (calculated as AE start date for the first occurrence – date of first IMP administration + 1). If a study participant has no events, the total time at risk is used.

Exact Poisson 95% CIs for incidence rates are calculated using the relationship between the Poisson and the Chi-square distribution (Ulm, 1990; Fay and Feuer, 1997):

$$LCL = \frac{\chi^2_{2n, \alpha/2}}{2 \times \sum_{i=1}^n (T_{Exp(i)})}$$

$$UCL = \frac{\chi^2_{2(n+1), 1-\alpha/2}}{2 \times \sum_{i=1}^n (T_{Exp(i)})}$$

where n is the number of study participants with a specific AE for the incidence rate of interest and is the basis for the number of the degrees of freedom for the chi-square quantile for the upper tail probability χ^2 .

The EAER will be the number of AEs including repeat occurrences in individual study participants divided by the total time at risk scaled to 100 participant-years and calculated using:

$$EAER = 100 \times N_{AE} / \sum_{i=1}^N (T_{Risk(i)})$$

where N_{AE} is the total number of AEs, T_{Risk} is the time at risk for each subject, and N is the total number of subjects at risk.

No CI will be computed for EAER.

Selected summaries will include the risk difference between bimekizumab and placebo. The risk difference (RD) is calculated as:

$$RD = IP_{BKZ} - IP_{PBO}$$

where IP_{BKZ} is the incidence proportion for the bimekizumab-treated group and IP_{PBO} is the incidence proportion for the placebo group. Note that incidence proportion simply refers to the percentage of study participants within the specified treatment group that experienced a given AE.

The standard error (SE) for the risk difference is calculated as follows:

$$SE_{RD} = \sqrt{\left(IP_{BKZ} \times \left(\frac{1 - IP_{BKZ}}{n_{BKZ}} \right) \right) + \left(IP_{PBO} \times \left(\frac{1 - IP_{PBO}}{n_{PBO}} \right) \right)}$$

where n_{BKZ} is the number of study participants in the bimekizumab-treated group and n_{PBO} is the number of study participants in the placebo group.

The corresponding CI for the risk difference is as follows:

$$CI_{RD} = RD \pm Z_{1-\alpha/2} \times (SE_{RD})$$

where $Z_{1-\alpha/2}$ is the Z statistic for the corresponding level of alpha. For the risk difference CIs calculated in this SAP, 1.96 will be used (corresponding to a two-sided alpha of 0.05 and 95% CI). The risk difference and corresponding CI will be displayed as percentage.

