The following summary will be provided for the Initial and Maintenance Treatment Period (combined) for the AMS by trough plasma concentration tertiles:

- TEAEs and infection TEAEs (TEAEs which code to the SOC of “Infections and infestations”) will be summarized by bimekizumab trough plasma concentration tertiles based on Week 32 PK samples. Study participants with missing Week 32 PK samples will not be included.

The summary will include the number of TEAEs and infection TEAEs, number of study participants with TEAEs and infection TEAEs, percentage of study participants with TEAEs and infection TEAEs, EAIR with 95% CI, and EAER. Infection TEAEs will be sorted by SOC, High Level Group Term (HLGT), HLT and PT. Fungal infections and candida infections will be identified based on MedDRA classification; a separate table does not need to be produced to summarize these events.

In addition, all summaries of TEAEs based on “100 participant years” will include EAIR (with 95% CI) and EAER.

By-study participant listings on all AEs, all serious AEs, and all deaths will be provided on the ES. By-study participant listings based on TEAEs related to study medication and TEAEs leading to study discontinuation will be provided on the SS. A by-study participant listing for device deficiency will also be provided based on the SS.

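### The printed EAIR confidence limits use a different exposure sum and scale from the EAIR, so they are wrong in general and exclude the rate except when few participants have the event

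*SAP*

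**What the plan says.** SAP Section 4.5.2.1 (Data considerations) gives the rate as EAIR = 100 × n / Σ T_Exp(i), with the sum running from i = 1 to N, "where N is the total number of study participants in the respective treatment group". The rate is "adjusted for the exposure and will be scaled to 100 patient-years".

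Exposure for a participant with the event stops at the first occurrence. A participant without the event contributes the whole time at risk.

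The same section then says: "Exact Poisson 95% CIs for incidence rates are calculated using the relationship between the Poisson and the Chi-square distribution". In plain notation, the printed limits are:

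- LCL = χ²(2n, α/2) / (2 × Σ T_Exp(i)), sum from i = 1 to n
- UCL = χ²(2(n+1), 1−α/2) / (2 × Σ T_Exp(i)), sum from i = 1 to n

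The text below them reads "where n is the number of study participants with a specific AE for the incidence rate of interest". It adds that n drives the degrees of freedom, and it describes the chi-square quantile as one for the upper tail.

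The exposure-adjusted event rate (EAER) formula that follows sums to N and includes the factor of 100. Section 4.5.2.2 states that all TEAE summaries based on 100 participant years "will include EAIR (with 95% CI) and EAER". The same interval is called for in the TEAE tables by trough-concentration tertile (4.5.2.2) and by antibody status (4.6.1.4.2.4).

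**The concern.** A rate and its confidence limits must share a denominator and a unit. Here the rate uses everyone's exposure and is per 100 participant-years. The limits use only the exposure of participants who had the event and are per participant-year. Omitting the event-free participants inflates the limits; omitting the factor of 100 shrinks them. Only by coincidence would the two errors cancel.

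The SAP is the specification against which tables are programmed and checked. Code that follows these lines gives wrong intervals, and code that gives right intervals departs from the SAP. The affected tables include all TEAEs, serious TEAEs and TEAEs leading to permanent discontinuation of IMP. The incidences of these through Week 16 are listed as additional secondary endpoints.

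**Working it through.** The SAP gives no numerical EAIR or interval, so there is no stated figure to reproduce. The check applies the printed formulas to the planned group sizes.

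**Inputs from the SAP.** N = 90 (bimekizumab) and N = 30 (placebo), Section 1.2; 112 days in the Initial Treatment Period, Section 4.5.1.1; days divided by 365.25, Section 4.5.1; α = 0.05.

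**Assumptions, not in the documents.** Every event-free participant contributes 112 days. First events fall on average at a fraction f of the period; the base case is f = 0.5 and the range tried is 0.1 to 1.0.

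**Exposure sums.** With d = 112/365.25 = 0.3066 years:

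- S_N = (N − n + f·n) × d
- S_n = f·n × d
- Printed interval = correct interval × (S_N/S_n)/100

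With equal follow-up d cancels from S_N/S_n, so whether the printed interval contains the EAIR depends on n, N and f and not on the length of the period.

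**Worked case: N = 90, n = 9, f = 0.5.**

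- S_N = 85.5 × 0.3066 = 26.22; S_n = 4.5 × 0.3066 = 1.380
- EAIR = 100 × 9 / 26.22 = 34.33
- Lower-tail quantiles: χ²(18; 0.025) = 8.231 and χ²(20; 0.975) = 34.170
- Printed: 8.231/(2 × 1.380) = 2.98 and 34.170/(2 × 1.380) = 12.38
- Correct: 100 × 8.231/(2 × 26.22) = 15.70 and 100 × 34.170/(2 × 26.22) = 65.17
- Ratio check: (26.22/1.380)/100 = 0.19, and 0.19 × 15.70 = 2.98

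Repairing one slip alone does not help in this case. Summing to N without the 100 gives 0.157 to 0.652. Summing to n with the 100 gives 298.2 to 1238.1. Neither contains 34.33.

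**Other counts, f = 0.5.**

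| N | n | EAIR | Printed limits | Correct limits | Printed contains EAIR? |
|---|---|---|---|---|---|
| 90 | 1 | 3.64 | 0.17 to 36.34 | 0.09 to 20.30 | yes |
| 90 | 4 | 14.82 | 1.78 to 16.70 | 4.04 to 37.95 | yes |
| 90 | 5 | 18.64 | 2.12 to 15.22 | 6.05 to 43.49 | no |
| 90 | 30 | 130.45 | 4.40 to 9.31 | 88.01 to 186.22 | no |
| 30 | 2 | 22.49 | 0.79 to 23.56 | 2.72 to 81.24 | yes |
| 30 | 3 | 34.33 | 1.35 to 19.06 | 7.08 to 100.32 | no |

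**Sensitivity to event timing.** Largest n at which the printed interval still contains the EAIR:

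| f | 0.1 | 0.25 | 0.5 | 0.75 | 1.0 |
|---|---|---|---|---|---|
| N = 90 | 13 | 6 | 4 | 3 | 2 |
| N = 30 | 5 | 3 | 2 | 1 | 1 |

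Above these counts it excludes the rate in every scenario tried. The corrected interval contained the EAIR for every n from 1 to N.

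**Zero events.** At n = 0 the printed sum is empty, so the upper limit divides by zero. The corrected formula gives 100 × 7.378/(2 × 27.60) = 13.4 for N = 90 and 100 × 7.378/(2 × 9.199) = 40.1 for N = 30.

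**Tail wording.** If the subscripts were upper-tail probabilities, the limits would cross even after the other corrections: at N = 90, n = 9 the lower limit would be 60.1 and the upper 18.3. The subscripts work only as lower-tail (cumulative) probabilities.

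**The case against.** The strongest reply is that this is a notation slip whose intended meaning is clear. The section names the exact Poisson method, defines the rate over all N, and says what exposure to use for participants without events, which would be pointless if they were left out. It also gives n a job of its own, as the basis for the degrees of freedom. A programmer using standard exact-Poisson code would get the right limits. Literal code would often betray itself, through a rate outside its own interval or a division by zero. Misreading of N as n in the PDF text cannot be wholly excluded. The tail phrase is only loose wording, since the subscripts themselves are coherent.

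Much of this stands, and it lowers the severity. It does not remove the point: the lower-case index appears in both limits, the missing 100 does not depend on how that index was read, and no sentence in the SAP corrects either. Nor would every error be visible. At small n the literal interval can contain the rate and still be wrong, as at n = 1 of 90.

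A reader might infer something stronger: that the printed interval never contains its own rate. The formulas do not support that. When events are rare the two slips pull in opposite directions and the interval can still cover the EAIR, up to n = 13 of 90 if events come early. In a trial of about 120 participants, many preferred-term rows could have counts that small.

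**Conclusion.** The concern holds in this form: the limits printed in SAP Section 4.5.2.1 are on the wrong denominator and scale, are wrong in general, exclude the EAIR except when n is small, and leave the upper limit undefined at n = 0. The point at which exclusion begins rests on the assumptions of equal follow-up and event timing. The mismatch between the formulas does not; it can be read directly from the SAP.

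Severity is minor to moderate. A reader might also infer that the trial's safety comparison or efficacy conclusions are at risk. The documents do not support that. The EAIR and EAER point estimates are specified consistently, the bimekizumab-placebo risk differences have their own formulas, and no hypothesis test uses these limits. Nor do the documents show that any output was programmed from the literal formula.

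**What to change.** Replace the two limits in SAP Section 4.5.2.1 with:

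- LCL = 100 × χ²(2n; 0.025) / (2 × Σ T_Exp(i)), sum from i = 1 to N, and LCL = 0 when n = 0
- UCL = 100 × χ²(2(n+1); 0.975) / (2 × Σ T_Exp(i)), sum from i = 1 to N

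State that the quantiles are lower-tail (cumulative) and delete the upper-tail wording. Then check the table macro against the corrected formulas, including a row with n = 0 and one with a common event.

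The cost is a few characters in the SAP and a short programming check. Design, data collection and the rates themselves do not change. The SAP's version history already records corrections of the same kind, to the liver New Ratio formula and the adverse-event risk-difference formula.

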4.5.2.2 AE summaries

The following summaries will be provided in three different ways: by treatment for the ITP for the SS, by treatment for the MTP for the MS, by treatment for the Initial and Maintenance Treatment Period (combined) for the AMS. For summaries for the ITP, MTP, and Initial and Maintenance Period (combined), the TEAEs will be attributed according to their onset date and time at risk of each study participants for each period (see Section 4.5.1).

- Incidence of TEAEs – Overview
- Incidence of TEAEs per 100 participant years by SOC, HLT, and PT

The following summaries will be provided in two different ways: by treatment for the ITP for the SS, and by treatment for the Initial and Maintenance Treatment Period (combined) for the AMS:

- Incidence of Serious TEAEs per 100 participant years by SOC, HLT, and PT
- Incidence of TEAEs Leading to Permanent Discontinuation of IMP per 100 participant years by SOC, HLT, and PT
- Incidence of TEAEs Leading to Study Discontinuation per 100 participant years by SOC, HLT, and PT
- Incidence of TEAEs Leading to Death by SOC, HLT, and PT
- Incidence of TEAEs by Maximum Relationship by SOC, HLT, and PT
- Incidence of Serious TEAEs by Relationship SOC, HLT, and PT – Note: For EudraCT reporting purposes
- Incidence of TEAEs Leading to Death by Relationship by SOC, HLT, and PT – Note: For EudraCT reporting purposes
- Incidence of TEAEs by Maximum Intensity, SOC, HLT, and PT
- Incidence of TEAEs by decreasing frequency of PT
- Incidence of TEAEs Above Reporting Threshold of 5% by SOC and PT
- Incidence of Non-Serious TEAEs by SOC, HLT, and PT

- Incidence of Non-Serious TEAEs by Maximum Relationship SOC, HLT, and PT
- Incidence of Non-Serious TEAEs Above Reporting Threshold of 5% by SOC and PT
- Incidence of Non-Serious TEAEs Above Reporting Threshold of 5% by Relationship SOC and PT
- Incidence of Related TEAEs by SOC, HLT, and PT
- Incidence of Related TEAEs Above Reporting Threshold of 5% by SOC and PT

The following summary will be provided by treatment for the ITP for the SS:

- Incidence of TEAEs Above Reporting Threshold of 5% with Risk Differences by SOC and PT
- Incidence of Serious TEAEs and Risk Differences by SOC and PT

The tables with risk differences will also be accompanied by figures (dot plots) which show the incidence of the AEs and corresponding 95% risk difference CIs. These will be ordered by descending order of risk difference (bimekizumab vs placebo).

The following summary will be provided for the Initial and Maintenance Treatment Period (combined) for the AMS by trough plasma concentration tertiles:

- TEAEs and infection TEAEs (TEAEs which code to the SOC of “Infections and infestations”) will be summarized by bimekizumab trough plasma concentration tertiles based on Week 32 PK samples. Study participants with missing Week 32 PK samples will not be included.

The summary will include the number of TEAEs and infection TEAEs, number of study participants with TEAEs and infection TEAEs, percentage of study participants with TEAEs and infection TEAEs, EAIR with 95% CI, and EAER. Infection TEAEs will be sorted by SOC, High Level Group Term (HLGT), HLT and PT. Fungal infections and candida infections will be identified based on MedDRA classification; a separate table does not need to be produced to summarize these events.

In addition, all summaries of TEAEs based on “100 participant years” will include EAIR (with 95% CI) and EAER.

By-study participant listings on all AEs, all serious AEs, and all deaths will be provided on the ES. By-study participant listings based on TEAEs related to study medication and TEAEs leading to study discontinuation will be provided on the SS. A by-study participant listing for device deficiency will also be provided based on the SS.

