Note: After a study participant completes the Week 16 assessments, which are the last assessments of the Initial Treatment Period, the dose of IMP for the Maintenance Treatment Period will be administered according to the randomization scheme. The final assessments of the Maintenance Treatment Period will be performed at Week 32. No IMP will be administered at Week 32.

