1.2 Study design

PS0041 is a Phase 3, multicenter, randomized, double blind, placebo controlled, parallel group study to evaluate the efficacy and safety of bimekizumab in Chinese adult study participants with moderate to severe plaque PSO.

The study population consists of Chinese adult study participants (≥ 18 years of age) with a diagnosis of moderate to severe plaque PSO (Baseline PASI ≥ 12 and Body Surface Area [BSA] affected by PSO $\geq 10\%$ and Investigator's Global Assessment [IGA] score ≥ 3 on a 5-point scale) who are candidates for systemic PSO therapy and/or phototherapy.

This study will include 4 periods: Screening Period (up to 5 weeks), Initial Treatment Period (16 weeks), Maintenance Treatment Period (16 weeks), and Safety Follow-Up (SFU) Period (17 weeks after the final dose of IMP [Figure 1-1]).

• Screening Period

The Screening Period will last up to a total of maximum 5 weeks (for example, in cases where a laboratory assessment needs to be repeated or to allow washout of prohibited medications). During the Screening Period, eligible study participants will be informed about the study and sign the Informed Consent Form (ICF). Following signed informed consent, all screening procedures and laboratory tests (hematology, urine, and biochemistry) will be performed per the Protocol Schedule of Activities (SoA). A study participant newly diagnosed with a latent TB infection (LTBI) as a result of a positive Interferon-Gamma Release Assay (IGRA) screening test, may be rescreened once and enrolled after receiving ≥ 4 weeks of appropriate LTBI therapy and after consultation with the Medical Monitor. Further details of rescreening are provided in the exclusion criteria in the Protocol.

After completion of the Screening Period, eligible study participants will be allowed to enroll into the study.

• Initial Treatment Period

During the 16-week Initial Treatment Period, approximately 120 Chinese adult study participants will be randomized 3:1 to receive the following blinded IMP regimens:

- Bimekizumab 320mg administered sc every 4 weeks (Q4W) (90 study participants)

-
- Placebo administered sc Q4W (30 study participants)

IMP will be administered in the clinic by sc injection at the visits specified in the Protocol SoA. Study participants withdrawing early from the study will undergo the premature end of treatment (PEOT) visit assessments and will enter the SFU period.

- Maintenance Treatment Period

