After completion of the Week 16 assessments, which are the last assessments in the 16-week Initial Treatment Period, study participants will enter the 16-week Maintenance Treatment Period. The first dose of IMP will be administered at Week 16 after all assessments are performed. During the Maintenance Treatment Period, study participants will return to the clinic Q4W up to Week 32 to maintain the study blind.

The treatment during the Maintenance Treatment Period (Week 16 to Week 32) will be based on the following rules:

- Study participants in the bimekizumab 320mg Q4W arm will receive bimekizumab 320mg every 8 weeks (Q8W). These study participants will also receive placebo injections at visits between dosing with bimekizumab to maintain blinding procedures.
- Study participants in the placebo arm will receive bimekizumab 320mg Q4W.

[figure not shown]
- SFU Period

After completion of the 16-week Maintenance Treatment Period, study participants will enter the SFU Period after the final dose of IMP.

Study participants withdrawing early from the study will undergo the PEOT Visit assessments and will enter the SFU Period.

All study participants, including those withdrawn from IMP, will have a SFU Visit 17 weeks after the last dose of IMP.

Figure 1-1: Study schematic

IGA 0/1=Investigator's Global Assessment response clear (0) or almost clear (1) with ≥ 2 -category improvement relative to Baseline; PASI90=90% or greater improvement from Baseline in the Psoriasis Area and Severity Index score; Q4W=every 4 weeks; Q8W=every 8 weeks; w=week

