3 POPULATIONS FOR ANALYSIS

The Enrolled Set (ES) will consist of all study participants who have given informed consent.

The Randomized Set (RS) will consist of all randomized study participants.

The Safety Set (SS) will consist of all study participants who receive ≥ 1 dose of IMP (bimekizumab or placebo).

The Full Analysis Set (FAS) will consist of all randomized study participants who receive ≥ 1 dose of IMP and have a valid measurement for each of the co-primary efficacy endpoints at Baseline.

The Active Medication Set (AMS) will consist of all study participants who receive ≥ 1 dose of active IMP (bimekizumab).

The Maintenance Set (MS) will consist of all study participants who receive ≥ 1 dose of active IMP (bimekizumab) in the Maintenance Treatment Period.

The Per-Protocol Set (PPS) will consist of all study participants in the RS who have no important protocol deviations affecting the co-primary efficacy endpoints. Important protocol deviations

will be predefined, and study participants with important protocol deviations will be evaluated during ongoing data cleaning meetings prior to database lock. The classification of PPS will be determined at blinded data evaluation meeting before unblinding of the data. The classification of study participants with important protocol deviations related to treatment group information will be re-determined after general unblinding.

The Pharmacokinetics Per-Protocol Set (PK-PPS) will consist of all randomized study participants who receive ≥ 1 dose of active IMP (bimekizumab) and provide ≥ 1 quantifiable plasma concentration post dose without important protocol deviations that would affect the concentration.

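### Grouping TEAEs by one set of Week 32 trough tertiles mixes two regimens in the top tertile and classes Week 0–16 events by a later Q8W trough

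*SAP*

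**What the plan says.** SAP 4.5.2.2 plans one summary for the combined Initial and Maintenance Treatment Period, "for the AMS by trough plasma concentration tertiles". In it, TEAEs and infection TEAEs "will be summarized by bimekizumab trough plasma concentration tertiles based on Week 32 PK samples". The table shows event counts, participant counts and percentages, EAIR with 95% CI, and EAER. On missing samples: "Study participants with missing Week 32 PK samples will not be included".

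SAP section 3 defines the Active Medication Set as everyone with at least one bimekizumab dose, so both randomized arms are in it. SAP 1.2 gives the allocation: "approximately 120 Chinese adult study participants will be randomized 3:1 to receive the following blinded IMP regimens", that is 90 and 30. In maintenance the bimekizumab arm moves to Q8W, while "Study participants in the placebo arm will receive bimekizumab 320mg Q4W". Protocol Table 6-2 lists active doses at Weeks 0, 4, 8, 12, 16 and 24 for the first arm and at Weeks 16, 20, 24 and 28 for the second. Of the last visit, Protocol 6.1 says "No IMP will be administered at Week 32", so the Week 32 sample is a trough in both arms.

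The tertile summary is introduced by trough tertile, whereas the neighbouring AE summaries are introduced by treatment. No cut points within regimen, regimen split or caveat is given.

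**The concern.** A table of adverse events by concentration tertile is read for whether events become more frequent as concentration rises. That reading needs the tertiles to differ in concentration and in little else, and the concentration to represent the period in which the events occurred. Neither condition is met here.

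- **Regimen.** The two arms are sampled at different times after their last active dose, so switchers tend to have higher Week 32 troughs because of their schedule.
- **Follow-up.** Switchers contribute events only from Week 16, the other arm from Week 0.
- **Timing of exposure.** The Q4W/Q8W arm's first 16 weeks of events arose under Q4W dosing but are filed under a concentration measured 16 weeks later, under Q8W. This affects all three tertiles.

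At stake is the interpretation of the one planned AE table by concentration. Infections are a prespecified safety topic and are singled out in it. A flat or falling pattern across tertiles could be an artefact, and a real relation could be obscured.

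**Working it through.** **1. Arm sizes.** 120 × 3/4 = 90 and 120 × 1/4 = 30, as stated in SAP 1.2. With complete sampling, each pooled tertile holds 120/3 = 40, and switchers are 30/120 = 25% of the set.

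**2. Time since last active dose at Week 32 (Table 6-2).** Q4W/Q8W: 32 − 24 = 8 weeks. Placebo/Q4W: 32 − 28 = 4 weeks.

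**3. Planned time at risk for completers (SAP 4.5.1.2 and 4.5.1.3: last dose − first dose + 119 days).** The Week 28 injection is the last dose in both arms, since SAP 4.1 counts placebo injections in maintenance as IMP.
- Q4W/Q8W, from Week 0: 196 + 119 = 315 days.
- Placebo/Q4W, from Week 16: 84 + 119 = 203 days.
- Ratio: 315/203 = 1.55.

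**4. Expected trough ratio at Week 32.** Half-life and between-participant CV are not in the documents. Assumed: equal doses, first-order elimination, superposition, half-life h of 10 to 45 days, lognormal variability with CV 30 to 100%, the same in both arms. With times in weeks since each active dose and k = ln 2/h:

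ratio = [e^(−4k) + e^(−8k) + e^(−12k) + e^(−16k)] / [e^(−8k) + e^(−16k) + e^(−20k) + e^(−24k) + e^(−28k) + e^(−32k)]

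At h = 21 days this is 0.6416/0.1982 = 3.24. For h = 10, 14, 21, 28, 35 and 45 days it is 7.9, 4.9, 3.2, 2.5, 2.1 and 1.75.

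**5. Tertile make-up.** 4,000 simulated sets of 90 + 30, cut into pooled tertiles of 40. If trough were unrelated to arm, switchers would split 10/10/10.

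| Half-life, CV | Switchers low / middle / top | Switchers as share of top tertile |
|---|---|---|
| 14 d, 30% | 0 / 0 / 30 | 75% |
| 21 d, 50% | 0.1 / 2.3 / 27.6 | 69% |
| 28 d, 50% | 0.5 / 4.2 / 25.3 | 63% |
| 45 d, 100% (weakest) | 5.1 / 9.2 / 15.7 | 39% |

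Over the whole grid, 52 to 100% of switchers fall in the top tertile and form 39 to 75% of it. The low tertile is 87 to 100% Q4W/Q8W, the middle 77 to 100%.

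**6. Effect on crude percentages.** Give everyone the same constant hazard, so that concentration has no effect, and use 1 − exp(−rate × time at risk). At 1 per year the two arms show 57.8% (315 days) and 42.6% (203 days), a gap of 15.2 points.
- Full separation: the top tertile shows 0.75 × 42.6 + 0.25 × 57.8 = 46.4% against 57.8% in the other two, a deficit of 11.4 points.
- Weakest case, top versus low: (15.7 − 5.1)/40 × 15.2 = 4.0 points.
- At 2 per year with full separation: 82.2% versus 70.9%, again about 11 points.

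With full separation, participant-years are 40 × 315/365.25 = 34.5 in each lower tertile and (30 × 203 + 10 × 315)/365.25 = 25.3 in the top. Rates that divide by time at risk are equal across tertiles under the constant hazard, provided switchers' event times run from their first bimekizumab dose.

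**7. Misclassified exposure in the main arm.** At Week 16 the Q4W/Q8W arm has had doses 4, 8, 12 and 16 weeks earlier, the same numerator as in step 4. Its Week 16 trough is therefore expected to be 1.75 to 7.9 times its own Week 32 trough.

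**The case against.** **The SAP may already split the table by treatment.** SAP 4.5.2 says AE summaries are given by treatment group, and SAP 4.1.4 sets default Q4W, Q8W and Total columns for combined-period safety tables. The tertile text does not say whether these apply, so pooling is the natural reading rather than an explicit statement. If they do apply, a Q8W column would lie within one regimen. The Q4W column would still combine the bimekizumab arm's initial period with the switchers' maintenance period, and the Total column would still mix arms. Nothing says the cut points would be set within regimen. This narrows the point but does not remove it.

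**The rates adjust for follow-up.** This stands. A reader might infer that exposure length biases the whole table. The documents do not support that, because EAIR and EAER are reported. Length matters for counts and percentages, and for the rates only if the hazard changes with time since first dose.

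**The tertiles are not simply the arms.** This also stands. With 3:1 allocation the top tertile can hold at most 30 of 40 switchers, and low versus middle is close to a comparison within one arm.

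**Dropping participants without a Week 32 sample.** A reader might infer material selection bias, since participants who stopped for an AE can be lost. The documents give no basis for its size. SAP 4.1.3 maps an early-termination visit after Week 28 to Week 32, so some late stoppers are kept, and TEAEs leading to discontinuation are tabulated separately on the full Active Medication Set.

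**The table is descriptive.** No test or endpoint depends on it, and TEAE tables by treatment exist for each period. This limits the priority.

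**Conclusion.** The point holds in a limited form. Read as written, the rule produces a top tertile enriched for placebo switchers, so its comparison with the lower tertiles is confounded by regimen. The direction holds in every scenario examined. The degree, 39 to 75% switchers against 25% overall, rests on an assumed half-life, CV, elimination model and complete sampling. Crude percentages carry a spurious deficit at high concentration of about 4 to 11 points under an assumed hazard of 1 per year. The mismatch between Week 0–16 events and a Week 32 trough is separate and also affects the low-versus-middle comparison.

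It would go too far to say that switchers had half the bimekizumab exposure: they have half the planned treatment weeks (16 of 32) but 4 active doses against 6. Nor do the documents show that a true relation between concentration and adverse events will be masked or reversed, only that this table could not distinguish such a relation from a regimen effect. This is a modest-priority improvement to one descriptive table and does not affect the trial's efficacy conclusions or its main safety tables.

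**What to change.** In SAP 4.5.2.2, replace the single set of tertiles with tertiles cut and displayed within randomized regimen, and match the TEAE window to the sample:

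- Initial-period TEAEs in the bimekizumab arm by Week 16 trough tertile.
- Maintenance-period TEAEs by Week 32 trough tertile, separately for Q8W and placebo/Q4W.
- A separate row for participants without the relevant sample, giving their number and their TEAEs.

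A trough from another visit should not stand in for a missing one. Under the model above with a 21-day half-life, the Q8W arm's Week 24 trough is 0.2585/0.1982 = 1.30 times its Week 32 trough, and the switchers' is 0.5543/0.6416 = 0.86 times theirs, so substitution would mis-rank participants.

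Regimen and planned follow-up are then constant across the tertiles being compared. The Week 16 and Week 32 samples are already in the Schedule of Activities, so the cost is SAP wording and reprogramming one table. The drawback is small cells: with complete sampling, 90/3 = 30 per tertile in the bimekizumab arm but only 30/3 = 10 in the placebo/Q4W group, which is thin for a display by preferred term.
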